6.6.3 Dose modifications

For participants who do not tolerate the protocol-specified dosing schedule, dose interruptions, and/or reductions are either recommended or mandated in order to allow participants to continue the study treatment.

Table 6-3 Dose reduction schedule

*Dose reduction			
		Starting dose level 0	Dose level – 1
Asciminib	CML-CP	40 mg b.i.d. (total daily dose 80 mg)	20 mg b.i.d. (total daily dose 40 mg)
	CML-CP	80 mg q.d. (total daily dose 80 mg)	40 mg q.d. (total daily dose 40 mg)
	CML-CP	200 mg q.d. (total daily dose 200 mg)	80 mg q.d. or 40 mg b.i.d. (total daily dose 80 mg)**
*Dose reduction should be based on the worst toxicity demonstrated at the last dose.			
**Patients on 200 mg q.d. needing a dose de-escalation will revert to 80 mg total daily dose of asciminib, according to pre-escalation dosing schedule (q.d. or b.i.d. regimen assigned at enrollment).			
Asciminib dose reduction below total daily dose of 40 mg (20 mg b.i.d. or 40 mg q.d.) is not allowed. 20 mg tablets will be dispensed to patients having 20 mg b.i.d. regimen in the instance of dose reduction.			

These dose modifications, in addition to permanent treatment discontinuations, are summarized in (Table 6-4). Deviations to mandatory dose interruptions and/or reductions are not allowed.

These dose changes must be recorded on the appropriate CRF.

A patient must discontinue treatment with asciminib if, after treatment is resumed at a lower dose level, the toxicity recurs with the same or worse severity, except for recurrence of cytopenias (Table 6-4). If a patient requires a dose interruption of > 28 days for each non-hematologic toxicity, then the patient must be discontinued from the study treatment. If a hematologic toxicity (cytopenia Grade 3 or 4) last for more than 42 days without recovery to at least a Grade 2, despite asciminib interruption and adequate management (including hematopoietic growth factors), then the patient must be discontinued from study treatment.

Table 6-4 Criteria for dose reduction / interruption / discontinuation and re-initiation of treatment for adverse drug reactions

Dose modifications for asciminib	
Please note that if a patient requires a dose interruption of > 28 days for any toxicity, and > 42 days for hematologic toxicity, then the patient should be discontinued from study treatment	
Worst toxicity CTCAE Version 5.0	Asciminib

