Grade 4	Mandatory: Permanently discontinue patient from treatment
Investigations (renal)	
Serum creatinine	
Grade 1 (> ULN - 1.5 x ULN)	Recommendation: Maintain dose level
Grade 2 (> 1.5 - 3.0 x ULN)	Recommendation: Hold dose until resolved to grade ≤ 1 or baseline, then maintain dose level
Grade 3 (> 3.0 - 6.0 x ULN)	Mandatory: Permanently discontinue patient from treatment
Grade 4 (> 6.0 x ULN)	Mandatory: Permanently discontinue patient from treatment
Investigations (hepatic)	
Isolated total bilirubin elevation	
> ULN – 1.5 x ULN, if baseline was normal	Recommendation: Maintain dose level
> 1.5 - 3.0 x ULN if baseline was normal	Recommendation: Maintain dose. Repeat Liver Function Tests (LFT) within 48-72 hours then monitor LFTs ^b weekly, or more frequently if clinically indicated, until resolved to ≤ 1.5 x ULN or baseline: if resolved in ≤ 14 days, then maintain dose level if resolved in > 14 days, then reduce dose ↓ 1 dose level
> 3.0 - 10.0 x ULN (irrespective of the baseline levels) *	Mandatory: Hold dose. Repeat LFTs within 48-72 hours then monitor LFTs ^b weekly, or more frequently if clinically indicated, until resolved to ≤ 1.5 x ULN or baseline: if resolved in ≤ 14 days, then reduce dose ↓ 1 dose level if resolved in > 14 days, then discontinue patient from treatment.

Dose modifications for asciminib	
Please note that if a patient requires a dose interruption of > 28 days for any toxicity, and > 42 days for hematologic toxicity, then the patient should be discontinued from study treatment	
Worst toxicity CTCAE Version 5.0	Asciminib
	The patient should be monitored weekly (including LFTs ^b), or more frequently if clinically indicated, until total bilirubin level has resolved to baseline or has stabilized over 4 weeks
> 10.0 x ULN (irrespective of the baseline levels) *	See footnote**** - otherwise discontinue study treatment The patient should be monitored weekly (including LFTs ^b), or more frequently if clinically indicated, until total bilirubin level has resolved to baseline or has stabilized over 4 weeks
Isolated AST or Alanine Aminotransferase (ALT) elevation	
If normal at baseline:	
> ULN - 3.0 x ULN	Recommendation: Maintain dose level Repeat liver tests within 48- 72 hours, then monitor weekly until recovery to ≤Grade 1 or to baseline

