> 3.0 - 5.0 x ULN	Recommendation: Maintain dose level. Repeat LFTs ^b as soon as possible, preferably within 48-72 hours from awareness of the abnormal results; if abnormal lab values are confirmed upon the repeat test, then monitor LFTs ^b weekly, or more frequently if clinically indicated, until resolved to ≤ 3.0 x ULN
> 5.0 - 10.0 x ULN	Mandatory: Omit dose. Repeat LFTs ^b as soon as possible, preferably within 48-72 hours from awareness of the abnormal results; monitor LFTs ^b weekly, or more frequently if clinically indicated, until resolved to ≤ 3.0 x ULN. Then: If resolved in ≤ 14 days, resume at prior dose level If resolved in > 14 days, resume with reduced dose ↓ 1 dose level
> 10.0 - 20.0 x ULN	Mandatory: Omit dose. Repeat LFTs ^b as soon as possible, preferably within 48-72 hours from awareness of the abnormal results; monitor LFTs ^b weekly, or more frequently if clinically indicated, until resolved to ≤ baseline. Then resume with reduced dose ↓ 1 dose level
> 20.0 x ULN	Mandatory: Permanently discontinue
If elevated at baseline:	
> Baseline - 3.0 x Baseline AND ≤ 5 x ULN	Recommendation: Maintain dose level
> 3.0 x Baseline AND > 5.0 x ULN (duration less than 2 weeks)	Recommendation: Maintain dose level. Repeat LFTs ^b as soon as possible, preferably within 48-72 hours from awareness of the abnormal results; if abnormal lab values are confirmed upon the repeat test, then monitor LFTs ^b weekly, or more frequently if clinically indicated, until resolved to ≤ ULN or baseline
> 3.0 x Baseline AND > 5.0 x ULN (duration more than 2 weeks):	Mandatory: Omit dose. Repeat LFTs ^b as soon as possible, preferably within 48-72 hours from awareness of the abnormal results; if abnormal lab values are confirmed upon the repeat test, then monitor LFTs ^b weekly, or more frequently if clinically indicated, until resolved to ≤ ULN or baseline. If resolved, resume with reduced ↓ 1 dose level.
> 5.0 x Baseline AND > 8.0 x ULN (irrespective of the duration):	Mandatory: Omit dose. Repeat LFTs ^b as soon as possible, preferably within 48-72 hours from awareness of the abnormal results; if abnormal lab values are confirmed upon the repeat test, then monitor LFTs ^b weekly, or more frequently if clinically indicated, until resolved to ≤ ULN or baseline. If resolved, resume with reduced ↓ 1 dose level.
> 20.0 x ULN	Permanently discontinue
Combined ^c elevations of AST or ALT and total bilirubin	

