
Dose modifications for asciminib Please note that if a patient requires a dose interruption of > 28 days for any toxicity, and > 42 days for hematologic toxicity, then the patient should be discontinued from study treatment
	

Worst toxicity CTCAE Version 5.0
	
Asciminib

For patients with normal baseline ALT and AST and total bilirubin value:
 
AST or ALT > 3.0 x ULN combined with total bilirubin > 2.0 x ULN without evidence of cholestasis^d
 
For patients with elevated baseline AST or ALT or total bilirubin value [AST or ALT > 3 x baseline OR [AST or ALT > 8.0 x ULN], whichever is lower combined with total bilirubin > 2 x baseline AND > 2.0 x ULN
 
Note: For participants with Gilbert's syndrome, at least 2-fold increase in direct bilirubin
	
Mandatory: Hold dose
 
Repeat liver tests as soon as possible, preferably within 48 hours from awareness of the abnormal results, then with weekly monitoring of LFTs^b, or more frequently if clinically indicated, until AST, ALT, or bilirubin have resolved to baseline or stabilization over 4 weeks. Please refer to Section 6.6.4.1 for additional follow-up evaluations as applicable.
 
If DILI confirmed: permanently discontinue patient from study drug treatment
 
If not DILI – interrupt treatment. Treat identified cause according to institutional guidelines. If resolved, then reduce dose ↓ 1 dose level, if cause is treatment related.

Investigation (metabolic)
	

Amylase and/or lipase elevation
	

Grade 1: > ULN - 1.5 x ULN
	
Recommendation: Maintain dose level, measure 2x per week

Grade 2: > 1.5 - 2.0 x ULN; >2.0 - 5.0 x ULN and asymptomatic
	
Recommendation: Maintain dose level, measure 2x per week

Grade 3: > 2.0 - 5.0 x ULN with signs or symptoms; >5.0 x ULN and asymptomatic
	
Mandatory: Hold dose until resolved to Grade ≤ 1 or baseline, then: If resolved in ≤ 7 days, then reduce dose ↓ 1 dose level If resolved in > 7 days, then discontinue treatment and obtain appropriate imaging (i.e., MRI, CT scan, or ultrasound) **

Grade 4: > 5.0 x ULN and with signs or symptoms
	
Mandatory: Permanently discontinue patient from treatment. Obtain appropriate imaging (i.e., MRI, CT scan, or ultrasound) **

Vascular disorders
	

Hypertension
	

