Grade 2	Recommendation: Maintain dose level, but initiate/intensify appropriate skin toxicity therapy (such as antihistamines, topical corticosteroids and low-dose systemic corticosteroids)
Grade 3, despite skin toxicity therapy	Recommendation: Hold dose until resolved to grade ≤ 1, then: If resolved in ≤ 7 days, reduce dose ↓ 1 dose level If resolved in > 7 days (despite appropriate skin toxicity therapy), discontinue patient from treatment
Grade 4, despite skin toxicity therapy	Mandatory: Permanently discontinue patient from treatment
General disorders and administration site conditions	
Fatigue/Asthenia	
Grade 1 or 2	Recommendation: Maintain dose level
Grade 3	Recommendation: Hold dose until resolved to grade ≤ 1, then: If resolved in ≤ 7 days, maintain dose level If resolved in > 7 days, reduce dose ↓ 1 dose level

All dose modifications should be based on the worst preceding toxicity.
 
^a Common Terminology Criteria for Adverse Events (CTCAE Version 5.0).
 
^b Core LFTs consist of ALT, AST, total bilirubin (fractionated [direct and indirect], if total bilirubin > 2.0 x ULN), and alkaline phosphatase (ALP) (fractionated [quantification of isoforms], if ALP > 2.0 x ULN).
 
^c “Combined” defined as total bilirubin increase to the defined threshold concurrently with ALT/AST increase to the defined threshold.
 
If combined elevations of AST or ALT and total bilirubin do not meet the defined thresholds, please follow the instructions for isolated elevation of total bilirubin and isolated elevation of AST/ALT, and take a conservative action based on the degree of the elevations (e.g. discontinue treatment at the situation when hold dose is needed for one parameter and discontinue treatment is required for another parameter). After all elevations resolve to the defined thresholds that allow treatment re-initiation, re-start the treatment either at the same dose or at one dose lower if meeting a criterion for dose reduction.
	

Dose modifications for asciminib	
Please note that if a patient requires a dose interruption of > 28 days for any toxicity, and > 42 days for hematologic toxicity, then the patient should be discontinued from study treatment	
Worst toxicity CTCAE Version 5.0	Asciminib

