
^d “Cholestasis” defined as ALP elevation (> 2.0 x ULN and R value < 2) in patients
 
Note: The R value is calculated by dividing the ALT by the ALP, using multiples of the ULN for both values. It denotes whether the relative pattern of ALT and/or ALP elevation is due to cholestatic (R ≤ 2), hepatocellular (R ≥ 5), or mixed (R >2 and < 5) liver injury.
 
* Note: If total bilirubin > 3.0 x ULN is due to the indirect (non-conjugated) component only, and hemolysis as the etiology has been ruled out as per institutional guidelines (e.g., review of peripheral blood smear and haptoglobin determination), then ↓ 1 dose level and continue treatment at the discretion of the investigator.
 
** Note: A CT scan or other imaging study to assess the pancreas, liver, and gallbladder should be performed within 1 week of the first occurrence of any grade ≥ 3 amylase and/or lipase elevation. If asymptomatic grade 3 elevations of lipase and/or amylase occur again at the reduced dose, patients will be discontinued permanently from study treatment. If asymptomatic grade 2 re-occur at reduce dose, closed monitoring of lipase and amylase will be required.
 
*** Note: Antidiarrheal medication is recommended at the first sign of abdominal cramping, loose stools, or overt diarrhea.
 
**** Note: An isolated bilirubin elevation is not typical for drug-induced liver injury. Bilirubin can be elevated either as part of a “Hy’s law” constellation with a preceding elevation of ALT/AST, or as part of a cholestatic reaction with simultaneous elevation of other cholestatic parameters (ALP, GGT). Isolated bilirubin can be seen in conjunction with drugs that inhibit bilirubin conjugation or excretion, but both scenarios do not typically represent liver injury. Alternative causes of bilirubin elevation should therefore, be ruled out before basing dose modification decisions on bilirubin values alone.
	

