Note: The R value is calculated by dividing the ALT by the ALP, using multiples of the ULN for both values. It denotes whether the relative pattern of ALT and/or ALP elevation is due to cholestatic ($R \leq 2$), hepatocellular ($R \geq 5$), or mixed ($R > 2$ and < 5) liver injury. In clinical situations where it is suspected that ALP elevations are from an extrahepatic source, the GGT can be used if available. GGT may be less specific than ALP as a marker of cholestatic injury, since GGT can also be elevated by enzyme induction or by ethanol consumption. It is more sensitive than ALP for detecting bile duct injury. Table 6-5 provides guidance on specific

clinical and diagnostic assessments which can be performed to rule out possible alternative causes of observed Liver function test (LFT) abnormalities.

Table 6-5 Clinical and diagnostic assessments to rule out possible alternative causes of observed LFT abnormalities

Disease	Assessment
Hepatitis A, B, C, E	IgM anti-HAV; HBsAg, IgM & IgG anti-HBc, HBV DNA; anti-HCV, HCV Ribonucleic acid (RNA), IgM & IgG anti-HEV, HEV RNA
CMV, HSV, EBV infection	IgM & IgG anti-CMV, IgM & IgG anti-HSV; IgM & IgG anti-EBV
Autoimmune hepatitis	Antinuclear Antibodies (ANA) & Anti-Smooth Muscle Antibody (ASMA) titers, total IgM, IgG, IgE, IgA
Alcoholic hepatitis	Ethanol history, GGT, MCV, CD-transferrin
Nonalcoholic steatohepatitis	Ultrasound or MRI
Hypoxic/ ischemic hepatopathy	Medical history: acute or chronic congestive, heart failure, hypotension, hypoxia, hepatic venous occlusion. Ultrasound or MRI
Biliary tract disease	Ultrasound or MRI, ERCP as appropriate.
Wilson disease (if <40 yrs old)	Caeruloplasmin
Hemochromatosis	Ferritin, transferrin
Alpha-1-antitrypsin deficiency	Alpha-1-antitrypsin

Other causes should also be considered based upon patients’ medical history (hyperthyroidism / thyrotoxic hepatitis – T3, T4, TSH; cardiovascular disease / ischemic hepatitis – ECG, prior hypotensive episodes; Type 1 diabetes / glycogenic hepatitis).

Obtain PK sample to determine exposure to study treatment and metabolites.

Following appropriate causality assessments, as outlined above, the causality of the treatment is estimated as “probable” i.e. >50% likely, if it appears greater than all other possible causes of liver injury combined. The term “treatment-induced” indicates probably caused by the treatment, not by something else, and only such a case can be considered a DILI case and should be reported as an SAE.

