9.1 Discontinuation from study treatment and from study

9.1.1 Discontinuation from study treatment

Discontinuation of study treatment for a participant occurs when study treatment is permanently stopped for any reason (earlier than the planned completion of study drug administration) and can be initiated by either the participant or the investigator.

The investigator must discontinue study treatment for a given participant if, he/she believes that continuation would negatively impact the participant's well-being.

Study treatment must be discontinued under the following circumstances:

- Participant/guardian decision
- Pregnancy
- Use of prohibited treatment. Refer to [Section 6.2.2](#).
- Any situation in which continued study participation might result in a safety risk to the participant
- In the case of certain adverse events and re-occurrence of adverse events (see [Table 6-4](#))
- Major Protocol Deviation, or any other protocol deviation that results in a significant risk to the patient's safety.

In addition to the general discontinuation criteria, the following study specific criteria will also require discontinuation of study treatment:

- In the event of treatment failure the patient should be discontinued from the study treatment. The ELN criteria 2020 do not make provisions for treatment failure in 3rd line however they define that a level of BCR-ABL1 > 1% IS and failure to achieve CCyR is not sufficient for optimal survival. The following events will constitute 'treatment failure':
 - BCR-ABL1 >1% IS at 48 weeks after initiation of therapy or no complete cytogenetic response at 48 weeks.

- Patients fulfilling treatment failure criteria above but without alternative treatment options may however be continued on study drug if in the investigators opinion they are obtaining benefit from the drug. Patients with BCR-ABL 1 greater than 10% after 48 weeks of treatment or patients with signs of progression to AP and BC must however be discontinued.
- Patients with newly emerging T315I mutation and lack or loss of response. While asciminib has known activity against CML with additional T315I mutation, the recommended dose of 200 mg BID for the treatment of T315I is not in use in the study. In case a patient demonstrates a new T315I mutation on asciminib, patients should not continue in the study.

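### Table 6-4 puts no ceiling on peak ALT/AST when a combined ALT/AST and bilirubin elevation is judged treatment related but not DILI, although ALT/AST >20 x ULN without the combined thresholds is a permanent stop

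*Protocol*

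**What the plan says.** All of the dosing text is in Protocol section 6.6.3, mainly Table 6-4.

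- **Isolated ALT/AST elevation.** Above 20 x ULN with a normal baseline, the action is "Mandatory: Permanently discontinue". With an elevated baseline the cut-off and the action are the same, though not labelled mandatory. Neither row has a restart path or an exception by cause.
- **Combined elevation.** The row has lower bounds only. With a normal baseline it needs ALT or AST above 3 x ULN and bilirubin above 2 x ULN, without cholestasis. With an elevated baseline it needs ALT or AST above the lower of 3 x baseline and 8 x ULN, and bilirubin above both 2 x baseline and 2 x ULN. Dosing is held and liver tests are repeated. Confirmed DILI is a permanent stop. Otherwise the cause is treated, and then: "If resolved, then reduce dose ↓ 1 dose level, if cause is treatment related".
- **Footnote c.** "If combined elevations of AST or ALT and total bilirubin do not meet the defined thresholds, please follow the instructions for isolated elevation". The advice to take the more conservative of two actions is in the same sentence.
- **General limits.** "If a patient requires a dose interruption of > 28 days for each non-hematologic toxicity, then the patient must be discontinued". Toxicity that returns at the lower dose with the same or worse severity also ends treatment (cytopenias excepted), and no dose below 40 mg a day is allowed. A note under the table ties dose changes to the worst toxicity seen beforehand.

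Section 6.6.4.1 rates treatment as the probable cause, that is more than 50% likely, "if it appears greater than all other possible causes of liver injury combined". Only such a case counts as DILI.

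**The concern.** ALT above 20 x ULN with bilirubin above 2 x ULN is a worse liver event than the same ALT with near-normal bilirubin. Yet the milder event has a fixed stop, and the worse one has a line that allows the drug to be given again after an event the investigator attributes to it. What is at stake is the safety of a few patients.

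Reduction by one level is not always a low dose. Under Table 6-3, a patient who had escalated to 200 mg q.d. goes back to 80 mg a day, the full standard dose.

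**Working it through.** The documents give no figure to reproduce and no event rate, so the check traces the written rule.

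**Fixed inputs (chosen for illustration).** Peak ALT 25 x ULN; ALP 1 x ULN; interruption of 20 days, inside the 28-day limit; resolved; judged treatment related but not DILI; a lower dose level still available. Footnote c is read literally, so the isolated rows apply when the combined thresholds are not met. Bilirubin is in multiples of ULN.

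| Baseline | Peak bilirubin | Combined thresholds | Governing row | Action |
|---|---|---|---|---|
| Normal | 1.8 | 25 > 3 yes; 1.8 > 2 no | Isolated, 25 > 20 | Permanent stop |
| Normal | 2.0 | 25 > 3 yes; 2.0 > 2 no | Isolated, 25 > 20 | Permanent stop |
| Normal | 2.1 | 25 > 3 yes; 2.1 > 2 yes; no cholestasis | Combined, not DILI | Restart one level lower permitted |
| ALT 2, bilirubin 1 (x ULN) | 1.8 | 25 > min(3 x 2, 8) = 6 yes; 1.8 > 2 no | Isolated, 25 > 20 | Permanent stop |
| ALT 2, bilirubin 1 (x ULN) | 2.1 | 25 > 6 yes; 2.1 > 2 x 1 and > 2 yes | Combined, not DILI | Restart one level lower permitted |

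The action changes from stop to permitted restart between bilirubin 2.0 and 2.1 x ULN with a normal baseline, and between 1.8 and 2.1 in the elevated-baseline example.

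**Does other text close the gap?**

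1. *Cholestasis.* With a normal baseline, cholestasis takes the case out of the combined row and so restores the stop. It needs ALP above 2 x ULN and R = ALT/ALP below 2. At ALT 25 x ULN that means ALP above 25/2 = 12.5 x ULN; for any ALT above 20 x ULN it means ALP above 10 x ULN.
2. *Generic grade 4 stop for non-hematologic reactions.* It excludes toxicities that have their own section, and hepatic toxicity has one.
3. *28-day limit, recurrence rule and 40 mg floor.* They limit the length of the interruption, a second event and the dose. None limits the severity of the first event.
4. *Section 9.1.1.* "The investigator must discontinue study treatment for a given participant if, he/she believes that continuation would negatively impact" the participant's well-being. The same section separately requires a stop wherever staying in the study could put the participant at risk. Both depend on judgement. Its criterion for particular adverse events refers back to Table 6-4.

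**Size on the primary endpoint.** SAP section 2.5.3 counts any treatment discontinuation before week 48 as non-response. One patient among the planned 156 is 100/156 = 0.64 percentage points at most, and zero if that patient would not have been in MMR at week 48 anyway.

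**The case against.** The best counter-argument is the note under Table 6-4 on the worst preceding toxicity. A patient whose ALT peaked at 25 x ULN has exceeded 20 x ULN, so the note supports keeping the permanent stop. Footnote c also says when the isolated rows apply; it does not state that their stops lapse otherwise. Both points have force, and the trace above rests on the literal reading. But the note does not rank the rows, and the worst toxicity in such a patient is arguably the combined event, which leads back to the lenient line. The text leaves the question open.

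Second, the combined row is not lax overall. It requires a hold, early repeat tests and, where applicable, the section 6.6.4.1 work-up, and confirmed DILI ends treatment. Where the drug is judged the probable cause, both rows stop. What remains is an event to which the drug contributed without being the probable cause. The protocol does not define that group; it is inferred from the causality bar and from the row's own condition that the cause be treatment related. This makes the group narrow, but not empty.

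Three stronger readings are tempting and are not supported:

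- *That the protocol requires restart.* It permits it, and section 9.1.1 can override it.
- *That there is a second reversal for bilirubin above 3 and up to 10 x ULN*, because the isolated row there says "if resolved in > 14 days, then discontinue patient from treatment". That comparison depends on chosen recovery times and is qualified by the footnotes, one of which requires that other causes "be ruled out before basing dose modification decisions on bilirubin values alone".
- *That the stricter row should govern every combined elevation.* This would also permanently stop a patient who had recovered from an event with a proven non-drug cause.

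**Conclusion.** The point holds in a narrow form. For a combined elevation that meets the thresholds and is judged treatment related but not DILI, Table 6-4 permits restart with no ceiling on peak ALT/AST. Without the combined thresholds, ALT/AST above 20 x ULN is a permanent stop. Neither footnote c nor the worst-toxicity note settles which rule wins, and the remaining protections are general backstops.

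This rests on the literal reading of footnote c and on there being patients in the inferred group. Cases should be rare, though the documents give no rate. The trial's conclusion is unaffected. It is a low-priority safety clarification.

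**What to change.** Add one clause to the not-DILI, treatment-related line of the combined row: *unless peak ALT/AST was >20 x ULN, in which case permanently discontinue.* Leave footnote c, the DILI causality standard and the handling of cases with a proven non-drug cause as they are, and add no new bilirubin rule.

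No new assessment is needed. Section 14.1 requires a written amendment with sponsor and IRB/IEC approval, and health-authority approval where required, so the clause can go into the next amendment. The downside is that, rarely, one more patient is discontinued and, if this is before week 48, counted as a non-responder.
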